5.5 Criteria for Taking a Participant Off Protocol Therapy

Duration of therapy will depend on individual response, evidence of disease progression and tolerance. In the absence of treatment delays due to adverse event(s), treatment may continue for 12 cycles or until one of the following criteria applies:

- Disease progression
- Intercurrent illness that prevents further administration of treatment
- Unacceptable adverse event(s)
- Participant demonstrates an inability or unwillingness to comply with the oral medication regimen and/or documentation requirements

- Participant decides to withdraw from the protocol therapy
- General or specific changes in the participant's condition render the participant unacceptable for further treatment in the judgment of the treating investigator
- Recurrent toxicity (see section 6)
- Patient becomes pregnant or cannot comply with birth control requirements.

Participants will be removed from the protocol therapy when any of these criteria apply. The reason for removal from protocol therapy, and the date the participant was removed, must be documented in the case report form (CRF). Alternative care options will be discussed with the participant.

A QACT Treatment Ended/Off Study Form will be filled out when a participant is removed from protocol therapy. This form can be found on the QACT website or obtained from the QACT registration staff.

In the event of unusual or life-threatening complications, treating investigators must immediately notify the Overall PI, [name] at [contact] or [contact] ([name]).

5.6 **Duration of Follow Up**

Participants will be followed for 3 years from the initiation of treatment, until subsequent therapy or until removal from study or death, whichever occurs first. Participants removed from protocol therapy for unacceptable adverse event(s) will be followed until resolution or stabilization of the adverse event.

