5.7 Criteria for Taking a Participant Off Study

Participants will be removed from study when any of the following criteria apply:

- Lost to follow-up
- Withdrawal of consent for data submission
- Initiation of subsequent therapy
- Death
- Completion of all study procedures

The reason for taking a participant off study, and the date the participant was removed, must be documented in the case report form (CRF).

A QACT Treatment Ended/Off Study Form will be filled out when a participant comes off study. This form can be found on the QACT website or obtained from the QACT registration staff.

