7.3 Expedited Adverse Event Reporting

7.3.1 Investigators **must** report to the Overall PI any serious adverse event (SAE) that occurs after the initial dose of study treatment, during treatment, or within 30 days of the last dose of treatment on the local institutional SAE form.

Expedited Reporting by Investigator to Celgene

Serious adverse events (SAE) are defined above. The investigator must inform Celgene in writing using a Celgene SAE form or MEDWATCH 3500A form of any SAE within 24 hours of being aware of the event. The written report must be completed and supplied to Celgene by facsimile within 24 hours/1 business day. The initial report must be as complete as possible, including an assessment of the causal relationship between the event and the investigational product(s). Information not available at the time of the initial report (e.g., an end date for the adverse event or laboratory values received after the report) must be documented on a follow-up report. A final report to document resolution of the SAE is required. The Celgene tracking number (RV-CL-OTHER-PI-004617) and the institutional protocol number should be included on SAE reports (or on the fax cover letter) sent to Celgene. A copy of the fax transmission confirmation of the SAE report to Celgene should be attached to the SAE and retained with the patient records.

Celgene Drug Safety Contact Information: Celgene Corporation Global Drug Safety and Risk Management [name] [contact] E-mail: [contact]

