10. STUDY CALENDAR

Baseline evaluations are to be conducted within 1 week prior to start of protocol therapy. Scans and x-rays must be done \leq 4 weeks prior to the start of therapy. In the event that the participant's condition is deteriorating, laboratory evaluations should be repeated within 48 hours prior to initiation of the next cycle of therapy.

Assessments must be performed prior to administration of any study agent. Study assessments and agents should be administered within \pm 3 days of the protocol-specified date, unless otherwise noted.

	Pre- Study	C1 D1	C1 D15	C2 D1	C2 D15	C3 D1	C3 D15	C4 D1	C5 D1	C6 D1	C7 D1	C8 D1	C9 D1	C10 & 11 D1	C12 D1	Off Treatment ^l	Follow Up ^m
Lenalidomide		Х	Х	Х	Х	Х	Х	Х	Х	Х	Х	Х	Х	Х	Х		
Anticoagulation		Х	Х	Х	Х	Х	Х	Х	Х	Х	Х	Х	Х	Х	Х	X ^h	
Informed consent	Х																
Demographics	Х																
Medical history	Х																
Concurrent meds			Х														X
Physical exam	Х	Х	Х	Х		Х		Х		Х		Х	Х		Х	Х	Х
Vital signs ^a	Х	Х	Х	Х		Х		Х		Х		Х	Х		Х	Х	Х
Height	Х	Х	Х	Х		Х		Х		Х		Х	Х		Х		Х
Weight	Х	Х	Х	Х		Х		Х		Х		Х	Х		Х	Х	Х
Performance status	Х	Х		Х		Х		Х		Х		Х	Х		Х	Х	Х
CBC w/diff, plts	Х	$\mathbf{X}^{\mathbf{j}}$	Х	\mathbf{X}^{j}	X^k	Х	X^k	Х		Х		Х	Х		Х	Х	Х
Serum chemistry ^b	Х	Х	Х	Х	X^k	Х	X^k	Х		Х		Х	Х		Х	Х	Х
EKG	Х																
Bone marrow biopsy	\mathbf{X}^{i}																\mathbf{X}^{i}
Adverse event evaluation			Х														X
Tumor measurements ^c	Х					Х				Х			Х		Х	Х	Х
Radiologic evaluation ^d	Х					Х				х			Х		Х	х	Х
B-HCG ^e	X ^b	Х		Х		Х		Х		Х		Х	Х		Х		Х
Urine/ Plasma Assay for BRAF mutation ^f	Xe					Х				х					Х	Х	Х
Serum TNF-alpha ^g	Х					Х				X					Х	Х	Х

a: Temperature, BP, HR and O2 saturation by pulse oximetry at rest.

b: Albumin, alkaline phosphatase, total bilirubin, bicarbonate, BUN, calcium, chloride, creatinine, glucose, potassium, total protein, SGOT [AST], SGPT [ALT], sodium.

c: Tumor measurements are repeated at C3D1, C6D1, C9D1 and C12D1 and then every 3 months thereafter until month 24. After month 24 tumor assessments will occur every 6 months (+/- 2 weeks) until month 36 from treatment initiation. Documentation (preferably radiologic) must be provided for participants removed from study for progressive disease. A window of +/- 1 week is allowed prior to month 24 but tumor assessments must occur prior to dosing on the relevant cycle when active treatment is being administered

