- CBC with automated differential will be checked every 7 days (+/- 1 day) during cycles 1 and 2; local labs are acceptable. Labs only necessary if dose escalation occurs. Note, these labs can be obtained at a local laboratory. Window for labs is +/- 3 days. k:
- Window for end of treatment visit is +/-7 days from the date of last dose. 1:
- The first follow up visit will occur 3 months from the date of last dose and then every 3 months thereafter. Window for follow up visits is m: +/- 2 weeks.

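### SAEs are reportable to day 30 after the last dose, but no safety contact is scheduled near day 30, and a patient who starts new therapy may have none at all

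*Combined protocol and SAP*

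**What the plan says.** **Reporting duty.** Section 7.3.1 covers SAEs arising after the first dose, "during treatment, or within 30 days of the last dose of treatment on the local institutional SAE form". Section 7.1 separately makes pregnancies up to 28 days after the last dose immediately reportable.

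**Scheduled contacts after the last dose.** These come from the footnotes to the study calendar in Section 10:
- End of treatment (footnote l): "Window for end of treatment visit is +/-7 days from the date of last dose".
- Follow-up (footnote m): "The first follow up visit will occur 3 months from the date of last dose and then every 3 months thereafter". The window is 2 weeks either way.
- Disease assessment (footnote c): "Tumor measurements are repeated at C3D1, C6D1, C9D1 and C12D1 and then every 3 months thereafter until month 24". The window before month 24 is 1 week either way.
- Other study assessments may fall within 3 days either side "of the protocol-specified date, unless otherwise noted".

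**When follow-up stops.** Section 5.6 follows patients for 3 years, "until subsequent therapy or until removal from study or death, whichever occurs first". Section 5.7 lists "Initiation of subsequent therapy" among the reasons for taking a patient off study, and Section 1 also ends follow-up at new therapy. None of the three makes an exception for the 30-day SAE window.

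**Who is already covered.** Section 5.6 follows patients removed for an unacceptable adverse event until that event resolves or stabilises. Section 5.2.2 has patients evaluated weekly when toxicity delays a cycle, and Section 6 also provides for follow-up of toxicity.

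**The concern.** The protocol sets a 30-day reporting window but schedules no contact that would reveal events in most of it. For a patient still on study the cost is delay and poorer recall: Section 7.5 requires all adverse events to be reported, the calendar marks an adverse event evaluation at follow-up, and deaths are dated for overall survival (Section 11.1.4).

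The serious case is the patient who stops lenalidomide, typically for progression, and soon starts another treatment. That patient goes off study and has no later scheduled contact. The duty in 7.3.1 still applies, but only to events the investigator happens to hear about.

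Two safety outputs depend on those events:
- The DSMC referral in Section 13.4 is triggered by the first toxic death. If that death is not collected, there is no referral.
- Section 13.6(d) reports the proportion of patients with grade 3-4 toxicity for each toxicity code. With 12 patients, each proportion is sensitive to a single event.

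**Working it through.** The plan gives no figure to reproduce, so the check is day arithmetic on the calendar.

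**Inputs**
- 28-day cycles with dosing on days 1-21, and at most 12 cycles (Section 5.1).
- SAE window of 30 days (Section 7.3.1).
- End-of-treatment visit at last dose ±7 days, first follow-up visit at 3 months ±14 days, scans every 3 months after C12D1 ±7 days, other visits ±3 days (Section 10).
- Planned accrual of 12 (Section 13.2).
- Assumptions: no cycle delays, and 3 months = 91 days. Results with 84 days are in square brackets.

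**Patient who completes 12 cycles**
- C12D1 = 11 × 28 + 1 = day 309, and last dose = 309 + 20 = day 329.
- End-of-treatment visit = 329 ± 7 = days 322-336. The SAE window closes on day 329 + 30 = 359.
- Next scan = 309 + 91 ± 7 = days 393-407, which is 64-78 days after the last dose [57-71].
- First follow-up visit = 329 + 91 ± 14 = days 406-434, which is 77-105 days after the last dose [70-98].
- Reportable days after the end-of-treatment visit: 30 − 7 = 23 if it is held at +7, and all 30 if it is held on or before the last dose.
- Delay for an event on days 8-30, counted to the scan: 64 − 30 = 34 to 78 − 8 = 70 days [27-63]. Counted to the follow-up visit: 77 − 30 = 47 to 105 − 8 = 97 days [40-90].

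**Patient removed at C3D1**
- Last dose (C2D21) = 28 + 21 = day 49, and C3D1 = 2 × 28 + 1 = day 57. The patient is seen 8 days after the last dose (5-11 with the ±3-day window).
- Reportable days left: 30 − 8 = 22 (30 − 11 = 19 to 30 − 5 = 25). The window closes on day 79.
- First follow-up visit = 49 + 91 ± 14 = days 126-154, which is 77-105 days after the last dose [70-98].
- Delay for an event on days 9-30: 77 − 30 = 47 to 105 − 9 = 96 days [40-89]. If new therapy starts first, there is no later scheduled contact.

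**Effect on the safety summary.** One uncollected grade 3-4 event changes the proportion for that toxicity code by 1/12 = 0.083, or 8.3 percentage points. Section 13.6(d) has no 30-day cut-off, so an event recovered late can still be counted.

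**The case against.** The strongest reply is that no two rules conflict. Section 7.3.1 covers any SAE to day 30 with no off-study exception, and going off study does not cancel it. Section 12.2 adds that the DSMC may receive a summary of deaths within 30 days of intervention. In a single-center study, where alternative care is discussed at removal, the investigator may well hear of a serious event. The adverse event row of the calendar shows only two marks and may be a merged bar meaning continuous collection. Permanent loss needs several things together: new therapy before the next visit, a new SAE late in the window, removal for some other reason, and an investigator who never learns of the event.

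Much of this stands. The group at risk of permanent loss is narrow, and its size cannot be estimated from the documents. The 30-uncovered-days case needs an early end-of-treatment visit; returning diaries and unused drug at the end of a cycle points to a visit near +7, so 23 days is the more realistic figure for a completer. The program that controls lenalidomide dispensing (REMS) may already cover part of the pregnancy question, though its schedule after treatment is not in the documents. Section 13.6(d) is descriptive, and attribution is harder once another drug has started.

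It does not close the gap. The reporting duty and the DSMC death summary both need someone to learn of the event. Continuous collection is not a dated contact, and it does not reach a patient who is off study.

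**Conclusion.** The concern holds. A site could follow the calendar exactly and still never collect a reportable SAE or a toxic death. After an end-of-treatment visit held in its window, 23 to 30 of the 30 reportable days have no scheduled contact. For a patient removed at C3D1 the figure is about 22. The next scheduled contact is the scan on days 64-78 for a completer, or the follow-up visit on days 77-105. Taking 3 months as 84 days moves these about a week earlier and changes nothing of substance.

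Permanent loss is limited to patients who leave for new therapy; for the rest the cost is timeliness and recall. The number who switch within 30 days is not given and could be anywhere from 0 to 12. The effect is on safety ascertainment only. The primary response analysis, the decision rule and the sample size stand as they are. This change should be made because it is cheap and the safety referral rests on a single death.

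**What to change.** - **Section 10:** add a calendar footnote requiring one telephone safety contact at about day 30 after the last dose. It records SAEs, vital status and, for women of childbearing potential, any known or suspected pregnancy. Waive it if the patient is already being seen for toxicity at that time.
- **Sections 5.6 and 5.7:** add one line to each saying that this contact is still due if new therapy has started. The exception is a patient off study under "Withdrawal of consent for data submission".

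The cost is one footnote, two lines of text and at most 12 telephone calls.

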11. MEASUREMENT OF EFFECT

11.1 Definitions

Evaluable for toxicity: All participants who receive at least one dose of study treatment will be evaluable for toxicity from the time of their first treatment.

Evaluable for objective response: Any patient who receives at least one dose of lenalidomide will be considered evaluable for response. These participants will have their response classified according to the definitions stated below. Patients not evaluable for response will not be replaced by another protocol participant.

11.1.1 Methods for Evaluation of Disease

All measurements should be taken and recorded in metric notation using a ruler, calipers, or a digital measurement tool. All baseline evaluations should be performed as closely as possible to the beginning of treatment and never more than 4 weeks before the beginning of the treatment.

The same method of assessment and the same technique should be used to characterize each identified and reported lesion at baseline and during follow-up. Imaging-based evaluation is preferred to evaluation by clinical examination unless the lesion(s) being followed cannot be imaged but are assessable by clinical exam.

Clinical lesions. Clinical lesions will only be considered measurable when they are superficial (*e.g.*, skin nodules) and \geq 5 mm in diameter as assessed using calipers. In the case of skin lesions, documentation by color photography, including a ruler to estimate the size of the lesion, is recommended. Skin lesions are considered non-target lesions for response assessment and will be described qualitatively as resolved, improved, stable, or progressive.

PET/CT: this is the preferred method of evaluation for all patients. Because of the propensity of histiocyte disorders to involve the skin and the bones of the skull, the PET/CT should encompass the area from the scalp to the toes. If PET/CT is not covered by insurance, a CT of the chest, abdomen and pelvis in combination with a bone scan is an acceptable alternative.

MRI: MRI is required for all patients at baseline and must be repeated at specified timepoints only if abnormal at baseline or if normal at baseline but there is subsequent clinical suspicion of a CNS recurrence.

11.1.2 Response Criteria

In contrast to lymphoma or other malignancies the terms "remission" or "relapse" should be avoided. In accordance with the nature of LCH the following definitions should be applied to judge the effect of treatment. The response criteria stated below has been designed by the Histiocyte Society to be applied in therapeutic studies of LCH and should be used for therapeutic decisions:

Table 3 Definition of disease state by organ system

NON ACTIVE DISEASE (NAD)	no evidence of disease	resolution of all signs or symptoms
	regressive disease	regression of signs or symptoms, no new lesions
ACTIVE DISEASE (AD)	stable disease	persistence of signs of symptoms, no new lesions
	progressive disease	progression of signs or symptoms and/or appearance of new lesions

Definition of response criteria

Table 4 Three categories of overall response

BETTER	complete resolution	NAD
DEIIER	regression	AD better mixed new lesions in one site,
INTERMEDIATE		regression in another site
	Stable	Unchanged
WORSE	progression*	

* In isolated bone disease progression is defined as appearance of new bone lesions or lesions in other organs.

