Grade 4	 and reduce the dose of lenalidomide by 1 dose level at the start of the next cycle. Omitted doses are not made up. If Grade 4, discontinue lenalidomide. Remove patient from study.
Venous thrombosis/embolism ≥ Grade 3	 Hold (interrupt) lenalidomide and start therapeutic anticoagulation, if appropriate. If VTE occurs while patient is on therapeutic anti-coagulation (not counting aspirin) permanently discontinue treatment. Restart lenalidomide at investigator's discretion (maintain dose level). See Anticoagulation Consideration (Section 5.6.1.2)
Hyperthyroidism or hypothyroidism	 Omit lenalidomide for remainder of cycle, evaluate etiology, and initiate appropriate therapy. See Instructions for Initiation of a New Cycle and reduce the dose of lenalidomide by 1 dose level.
Other non- hematologic toxicity ≥ Grade 3	 Hold (interrupt) lenalidomide dose. Follow at least weekly. If the toxicity resolves to ≤ grade 2 prior to Day 21 of the current cycle, restart lenalidomide and continue through the scheduled Day 21 of the current cycle. Otherwise, omit for remainder of cycle. Omitted doses are not made up. For toxicity attributed to lenalidomide, reduce the lenalidomide dose by 1 dose level when restarting lenalidomide.

Table 4. Tumor Flare Reaction Treatment (TFR)

Treatment of TFR is up to the discretion of the investigator, depending upon the severity and clinical situation. It is suggested that Grades 1 and 2 TFR be treated with NSAIDs (i.e., ibuprofen 400 to 600 mg orally every 4 to 6 hours as needed), corticosteroids, and/or narcotic analgesics for pain management.

In mild to moderate (Grades 1 and 2) cases, it is suggested that study drug be continued along with symptomatic treatment as above. In more severe cases, study drug should be interrupted.

Tumor Flare Reaction (TFR) ^a Grades 1-2	 Continue lenalidomide, maintain dose level At the investigator's discretion may initiate therapy with NSAIDs, limited duration corticosteroids, and/or narcotics
Grades 3-4	 Hold (interrupt dose) and initiate therapy with NSAIDs, corticosteroids, and/or narcotics When symptoms resolve to ≤ Grade 1, restart at same dose level for the rest of the Cycle

Treatment of Overdose

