7.1 Adverse Event List(s) for lenalidomide

The most frequently reported adverse events reported during clinical studies with lenalidomide in oncologic and non-oncologic indications, regardless of presumed relationship to study medication include: anemia, neutropenia, thrombocytopenia and pancytopenia, abdominal pain, nausea, vomiting and diarrhea, dehydration, rash, itching, infections, sepsis, pneumonia, UTI, Upper respiratory infection, atrial fibrillation, congestive heart failure, myocardial infarction,

chest pain, weakness, hypotension, hypercalcemia, hyperglycemia, back pain, bone pain, generalized pain, dizziness, mental status changes, syncope, renal failure, dyspnea, pleural effusion, pulmonary embolism, deep vein thrombosis, CVA, convulsions, dizziness, spinal cord compression, syncope, disease progression, death not specified and fractures.

Second New Cancers

In clinical studies of newly diagnosed multiple myeloma, a higher number of second cancers were reported in patients treated with lenalidomide as induction therapy (treatment for several cycles to reduce number of cancer cells) and/or bone marrow transplant followed by lenalidomide for a long period of time compared to patients treated with induction therapy and/or bone marrow transplant then placebo (a capsule containing no lenalidomide). Patients should make their doctors aware of their medical history and any concerns they may have regarding their own increased risk of other cancers.

Tumor Flare

Tumor flare assessments are conducted in Cycle 1 on Days 1, 8, and 15 (±1 day), and when clinically indicated thereafter. Tumor flare reaction (TFR) is defined in the NCI-CTCAE version 3 as a constellation of signs and symptoms of tumor pain, inflammation of visible tumor, hypercalcemia, diffuse bone pain, and other electrolyte disturbances in direct relation to initiation of therapy (Cancer therapy evaluation program, 2003).

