11.1.2.1 Evaluation of Target Lesions

Unfortunately the Histiocyte Society does not specify what constitutes radiographic regression or progression of disease. Since histiocyte disorders are hematologic malignancies we will use modified Cheson criteria to assign response as outlined below.

Response	Definition	Nodal Masses	Spleen and Liver	Bone Marrow
CR	Disappearance of all evidence of disease	 (a) FDG-avid or PET positive prior to therapy; mass of any size permitted if PET negative (b) Variably FDG-avid or PET negative; regression to normal size on CT 	Not palpable, nodules disappeared	Infiltrate cleared on repeat biopsy; if indeterminate by morphology, immunohistochemistry should be negative
PR	Regression of measurable disease and no new sites	 ≥50% decrease in SPD of up to 6 largest dominant masses; no increase in size of other nodes (a) FDG-avid or PET positive prior to therapy; one or more PET positive at previously involved site (b) Variably FDG-avid or PET negative; regression on CT 	≥50% decrease in SPD of nodules (for single nodule in greatest transverse diameter); no increase in size of liver or spleen	Irrelevant if positive prior to therapy
SD	Failure to attain CR/PR or PD	 (a) FDG-avid or PET positive prior to therapy; PET positive at prior sites of disease and no new sites on CT or PET (b) Variably FDG-avid or PET negative; no change in size of previous lesions on CT 	Any but PD below	Any but PD below
PD	Any new lesion or increase by _ 50% of previously involved sites from nadir	Appearance of a new lesion(s) > 1.5 cm in any axis, ≥ 50% increase in SPD of more than one node, or ≥50% increase in longest diameter of a previously identified node > 1 cm in short axis Lesions PET positive if FDG-avid lymphoma or PET positive prior to therapy	>50% increase from nadir in the SPD of any previous lesions	New or recurrent involvement

Deauville Criteria for PET scan interpretation in lymphoma will be used in this study as outlined below:

Five-point scale:

1. No Uptake

2. Uptake \leq mediastinum

3. Uptake >mediastinum but \leq liver

4. Uptake moderately increased compared to liver at any site

5. Uptake markedly increased compared to the liver at any site or/and new sites of disease

A score of 1-3 is PET NEGATIVE. A score of 4-5 is PET POSITIVE.

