13.5 Analysis of Primary Endpoints

The primary endpoint will be the proportion of responders. A responder is defined as an eligible, evaluable participant who achieves either complete resolution or regression of disease, per section 7, as the best overall response at any point during study therapy.

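### Section 11.1.2 contains two response systems with no ranking between them, so a change in symptoms alone could be read as response or as progression

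*Combined protocol and SAP*

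**What the plan says.** Two sets of criteria stand side by side in the response section.

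- **Histiocyte Society tables (11.1.2).** The section introduces them by saying that "the following definitions should be applied to judge the effect of treatment". Its Table 3 defines regressive disease as "regression of signs or symptoms, no new lesions" and progressive disease as "progression of signs or symptoms and/or appearance of new lesions". Its Table 4 places regression in the favourable category. A footnote makes one exception: "In isolated bone disease progression is defined as appearance of new bone lesions or lesions in other organs".
- **Modified Cheson criteria (11.1.2.1).** Because the Society gives no radiographic thresholds, "we will use modified Cheson criteria to assign response as outlined below". Stable disease is then whatever meets neither CR/PR nor PD, so unchanged scans are SD. The columns cover nodal masses, spleen and liver, and bone marrow. Skin is measured separately in 11.1.2.2.

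The primary endpoint (13.5) counts a participant who "achieves either complete resolution or regression of disease, per section 7". Section 7 is the adverse event section.

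On flare, 7.1 describes "a constellation of signs and symptoms of tumor pain, inflammation of visible tumor, hypercalcemia, diffuse bone pain" and other disturbances tied to the start of therapy. For grades 1-2 the flare table in Section 6 says "Continue lenalidomide, maintain dose level"; for grades 3-4 it interrupts and then restarts. Section 5.5 lists disease progression among the reasons for ending protocol therapy.

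**The concern.** Symptoms and scans can disagree in either direction, and the plan does not say how to score the disagreement.

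- **Towards response.** A patient with less pain and unchanged PET/CT is regressive, and so improved, in the Histiocyte Society tables, but SD in the Cheson table. The wording of 13.5 matches the former. In an open-label single-arm trial, symptom reports are open to expectation.
- **Towards progression.** The signs and symptoms of flare overlap the literal definition of progressive disease, and the response rules have no flare exception. Best overall response stops accruing at progression (11.1.2.3). A flare called progression in cycle 1 would therefore fix a non-response and an early PFS event before any scheduled scan. It would also set 5.5, which ends therapy, against the flare table, which continues or restarts it.

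The decision rests on three or more responders among 12, so a single classification can decide it.

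**Working it through.** **1. The plan's own figures.** Clopper-Pearson two-sided 90% limits are 7.19% to 52.73% for 3/12 (13.1 states 7-53%) and 3.05% to 43.81% for 2/12. The second interval contains 5% and the first does not. Both agree with 13.1.

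**2. Weight of one patient.** 1/12 = 8.3 percentage points. Moving from 2 to 3 responders crosses the rule.

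**3. Chance of meeting the rule.** P(X ≥ 3) = 1 − Σ(k=0 to 2) C(12,k) p^k (1−p)^(12−k).

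At the 5% that 13.1 calls unworthy: 1 − (0.54036 + 0.34128 + 0.09879) = 0.0196.

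**4. Symptom-only responses (assumed rates).** The documents give no rate. Let s be the share of lesion-based non-responders who count on symptoms alone. The apparent rate is 0.05 + 0.95s.

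| s (assumed) | Apparent rate | P(≥3 of 12) |
|---|---|---|
| 0 | 5% | 0.020 |
| 5% | 9.75% | 0.105 |
| 10% | 14.5% | 0.247 |
| 20% | 24% | 0.578 |

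**5. Responders lost to an early flare call (assumed rates).** Let f be the share of true responders scored as progression in cycle 1. The apparent rate is p(1−f).

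| f (assumed) | True rate 25% | True rate 30% |
|---|---|---|
| 0 | 0.609 | 0.747 |
| 5% | 0.570 | 0.710 |
| 10% | 0.528 | 0.669 |
| 20% | 0.442 | 0.578 |

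**6. Timing of flare.** Section 7.1 puts onset mostly in the first 2 to 3 weeks and resolution usually after a further 1 to 2 weeks. That gives an end between day 14 + 7 = 21 and day 21 + 14 = 35. C3D1 is day 2 × 28 + 1 = 57, or day 50 at the early edge of its one-week window. A typical flare is over by then. Only a clinical call before C3D1 would record it as progression.

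**7. Can such a call be made?** Yes. Section 7.1 schedules flare assessments on days 1, 8 and 15 of cycle 1, and the study calendar has a physical examination at C1D15. Footnote c of the calendar prefers radiologic documentation of progression but does not require it.

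**The case against.** The strongest reply is that the plan, read as a whole, is already lesion-based. Section 11.1.2.3 makes best response depend on measurement as well as confirmation, and asks for 8 weeks' maintenance. Duration of response (11.1.3) starts when measurement criteria for CR or PR are met. Section 11.1.1 prefers imaging to clinical examination, 11.1.5 provides central radiology review, and entry requires disease visible on imaging. The Cheson table can be read as supplying the thresholds that the Society's tables lack. The terms in 13.5 also match the measured skin categories in 11.1.2.2. This favours the lesion-based reading, but it does not settle the matter. A preference is not a rule of precedence, an 8-week requirement does not exclude symptom relief lasting 8 weeks, and central review covers radiology while the clinician adds clinical data with no rule for disagreement.

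A reader might go further and infer that flare is expected here and will be scored as progression. The documents do not support that. Section 1 calls its incidence in this population unknown. Section 6 handles flare separately from other adverse events, and no rule scores it as progression. In isolated bone disease the footnote requires new lesions.

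A reader might also infer that analgesics or corticosteroids given for flare would manufacture responses. Section 5.4 generally takes patients off protocol for glucocorticoid use unless it is expected to last under 7 days and not to recur. That fits poorly with a response that must last 8 weeks.

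Finally, the misclassification rates above have no source in the documents. That is correct, and they are shown as ranges for that reason.

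**Conclusion.** The point holds as an unresolved conflict that reaches the primary endpoint. Two response systems can give different answers for the same patient, neither is ranked above the other, and the sentence that should choose between them has a wrong cross-reference. Nothing in the response rules separates flare from progression.

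It would go too far to say that symptom relief does score as response or that flare does score as progression. Each is a possible literal reading, and the measurement and 8-week requirements in 11.1.2.3 weigh against the first. The flare risk is confined to clinical calls before C3D1 in patients without isolated bone disease.

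The firm quantity is 8.3 points per patient against a threshold of 3 in 12. The probabilities in steps 4 and 5 show how sensitive the rule is under assumed rates. They do not estimate what will happen.

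**What to change.** **Section 13.5.** Change the pointer from section 7 to section 11. State that, for endpoint scoring, a responder needs CR or PR by the lesion-based criteria: 11.1.2.1 with central review, and 11.1.2.2 for skin. Apply the same imaging-based assessment to bone and CNS lesions, which the Cheson columns do not list; without this, patients with mainly such disease would be hard to classify.

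**Section 11.1.2.** State that symptoms are recorded but are not sufficient alone for regression. State also that, for endpoint scoring, signs or symptoms recorded as tumor flare in cycle 1 are not progression on their own. Progression shown by imaging or new lesions, or death, counts whenever it occurs, so a true early progression is not deferred to C3D1.

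**Reconciliation.** Section 5.5, Table 3 of 11.1.2 and Table 4 of Section 6 must be made consistent on treatment during flare. No clinical rule is proposed here.

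**Cost.** Wording only, with no added visits or scans, although the bone and CNS wording needs some care. Purely symptomatic benefit would be reported descriptively and would not count towards the response rate.
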